#### 5.5.3.1.3 5-point IGA

A 5-point Investigator's Global Assessment (IGA) scale will be used to assess disease severity at Days -28, 0, 28, 56, 84, 112, 140, 168 and 196, or Premature Termination Visit, if applicable.

#### 5.5.3.1.4 Patient Global Impression of Change (PGIC)

A PGIC scale will be used to assess disease severity changes at Days 28, 56, 84, 112, 140, 168 and 196, or Premature Termination Visit, if applicable.

#### 5.5.3.1.5 Patient's Global Assessment using a VAS

A Patient's Global Assessment scale of disease severity evaluating skin fragility using a VAS will be used at Days -28, 0, 28, 56, 84, 112, 140, 168 and 196, or Premature Termination Visit, if applicable.

#### 5.5.3.1.6 Skin Mapping Photography

A mapping of the skin will be performed at Days -28, 0, 28, 56, 84, 112, 140, 168 and 196, or Premature Termination Visit,

#### 5.5.3.1.7 Skin Lesions Count

The number of skin lesions

will be assessed at Days -28, 0, 28, 56, 84 112, 140, 168 and 196, or Premature Termination Visit, if applicable.

[figure not shown]
5.	.5	.3.	.1.	8.	$\mathbf{C}$	)ua	litv	of	Life	
$\sim$		•••		• •	$\sim$	uu	LILY	O1		

The patient's Quality of Life, will be assessed at Days -28, 0, 28, 56, 84, 112, 140, 168 and 196, or Premature Termination Visit, if applicable.

#### 5.5.3.2 Safety variables

The number of participants with TEAEs will be summarised by MedDRA preferred term and body system. TEAEs will be further summarised by intensity, seriousness, outcome and relationship to study drug. Participants who prematurely terminate treatment due to AEs related to study medication will be summarised.

#### 5.5.3.2.1 Clinical Laboratory Evaluations

The Investigator will sign and date all laboratory reports and review all laboratory test results. The Investigator will evaluate the clinical significance of all values outside the reference range and will document within the laboratory report as well as in the patient's CRF. If a laboratory value is outside the reference range and felt to represent a clinically significant change from the baseline value, this will be reported as an AE in the patient's medical notes and on the AE CRF page. Clinically significant is defined as a change in the patient's clinical status that is regarded as important, whether or not it is due to the Investigational Medicinal Product. An assessment of this AE will be made by the Investigator, in particular regarding the relationship and seriousness of the event to the study drug.

#### 5.5.3.2.2 Physical Examination

A general physical examination will be performed

5.5.3.2.3 Weight and Height
Weight in kilograms (kg) will be recorded
5.5.3.2.4 Vital Signs Measurements
Vital signs (blood pressure, temperature and pulse rate) will be recorded
5.5.3.2.5 Dermatology Examination and Full Body Photography
Examination of the skin and oral mucosa and full body photography will be performed
5.5.3.2.6 Adverse Events
An adverse event (AE) is defined as any untoward medical occurrence in a patient or clinical
investigation subject administered a pharmaceutical product and which does not necessarily have to
have a causal relationship with this treatment. An AE may be a symptom, sign, or abnormal finding
or test result. Whenever possible, the Investigator will group together into a single term, signs and
symptoms that constitute a single diagnosis. For example, cough, rhinitis and sneezing might be
grouped together as "upper respiratory tract infection".
The Investigator will monitor each patient closely for the development of AEs, and any adverse event
spontaneously reported by or elicited from the patient itself or observed by the Investigators
(physician or study staff) will be recorded in the patient's medical notes and on the appropriate AE
page of the CRF, when applicable.

It is the responsibility of any member of the study site staff to immediately report any suspected AE to the Investigator.

The Investigator will assess the AE(s) in the patient's medical notes and provide the date and time of onset, severity, seriousness, action taken, outcome, date of resolution (or comment that the event is still continuing) and relationship to study medication.

An Adverse Drug Reaction is a noxious and unintended response to a medicinal product related to any dose.

All AEs will be followed up. AEs will be graded for severity as defined below:

- Mild The AE is transient and easily tolerated by the patient. Specific action is optional.
- Moderate The AE causes the patient discomfort and interrupts the patient's usual activities.
- Severe The AE causes considerable interference, preventing the patient's usual activities.

Outcome of the event must be described as one of the following:

- Recovered without sequelae;
- Recovered with sequelae;
- Recovering;
- Not recovered;
- Death.

The Investigator will be asked to document his/her opinion of the relationship of the event to the study drug as follows:

- **Related** There are facts or arguments to suggest a causal relationship, i.e. there is a reasonable possibility of a causal relationship between the drug and the AE(s).
- **Not Related** There is not a reasonable possibility that the AE(s) is/are related to the drug alternative aetiology, diagnosis, or explanations for the AE(s) exist, or the time from suspect drug intake make a relationship improbable.

Not Assessable - Report suggesting an adverse reaction BUT cannot be judged because
information is insufficient or contradictory OR cannot be supplemented or verified. Nonassessable cases by the site will be assessed by CLINUVEL and reported if deemed related to
study drug.

#### **Serious Adverse Events**

A Serious Adverse Event (SAE) is any adverse event occurring at any dose that results in any of the following outcomes:

- Death (due to any cause);
- Is life-threatening;
- Requires inpatient hospitalisation or a prolongation of an existing hospitalisation;
- Results in a persistent or significant disability/incapacity;
- Is a congenital anomaly/birth defect;
- Important medical events that may not be immediately life threatening, result in death or require hospitalisation but may be considered a serious adverse event when, based upon appropriate medical judgment, they may jeopardise the patient or may require medical or surgical intervention to prevent one of the outcomes listed in the definition above.

**Reporting**: Any SAE, including death due to any cause, which occurs during this study, has to be reported to CLINUVEL within 24 hours of the Investigator or their delegate becoming aware of the event, even if only limited information regarding the event is available.

[figure not shown]
In the event that the investigator becomes aware of an SAE which is thought to be related to the IMP, even months or years after the end of the clinical trial, it should be reported to the sponsor.

A SAE report form will be completed and sent to CLINUVEL Safety Team at

or fax to the number provided in the CUV040 SOM within 24 hours of the event occurring or within 24 hours of becoming aware of the event. In addition to completing the SAE report form (one form completed for each case), additional supporting information should be provided as appropriate, such as photocopies of pertinent test results and medical notes, trial records, consultant report(s), hospital discharge summary and autopsy report (if relevant and as soon as available to the Investigator). All SAEs will be recorded in the patient's medical notes and on the AE page of the CRF.

The Investigator will determine whether the seriousness of the event warrants removal of any patient from the study. The Investigator will institute appropriate diagnostic and therapeutic measures and keep the patient under observation for as long as is medically indicated.

Certain AEs and/or SAEs, including suspected unexpected serious adverse reactions (SUSARs), may warrant expediting to IECs, according to the regulatory requirements for the individual countries or sites involved, either by the Investigator or the Sponsor. The modalities for reporting and filing relevant documentation will be detailed in the CUV040 SOM.

#### Pregnancy and/or Breastfeeding

The following situations must be reported to CLINUVEL within 24 hours of the Investigator or their delegate becoming aware of the event, even if only limited information regarding the event is available.

- Pregnancy occurring in a female patient, when the start of the pregnancy is less than three months after the last afamelanotide implant was administered;
- Pregnancy occurring in the female partner of a male patient treated, when the start of the pregnancy is less than three months after the last afamelanotide implant was administered to the male patient;
- Female patient breastfeeding when the start of breastfeeding is less than three months after the last afamelanotide implant was administered;
- Birth of a child from a female patient, when the start of the pregnancy was less than three months after the last afamelanotide implant was administered;
- Birth of a child from the female partner of a male patient, when the start of the pregnancy is less than three months after the last afamelanotide implant was administered to the male patient.

Report Form and/or a Pregnancy Outcome/Breastfeeding Report form will be completed and sent to CLINUVEL Safety Team at \_\_\_\_\_\_ or fax to the number provided in the CUV040 SOM within 24 hours of becoming aware of the event. All pregnancies will be followed from the date of pregnancy detection until pregnancy outcome and/or lactation and breastfeeding (when applicable).

Female patients who become pregnant, give birth or begin breastfeeding during the treatment period will be withdrawn from treatment and complete the Premature Termination and Follow-Up Visits.

For male patients of female partners who become pregnant, the responsible Investigator will determine whether the event warrants removal of any patient from the study.

#### **Documentation and submission:**

The sponsor ensures to keep detailed records of all AEs which are reported to him by the investigators. Submission of SUSARs to the ethics committee (EC) and regulatory authorities will follow pertinent national legislation.

These events are in particular:

[figure not shown]
- single cases of expected SADRs with an unexpected outcome,
- an increased incidence of expected SADRs considered clinically significant,
- SUSARs occurring after a concerned person has completed the trial,
- events related to the conduct of the trial or the development of the investigational medicinal product possibly affecting the safety of the concerned persons.

All additional measures deemed necessary through new findings and taken by the Sponsor or the investigator to protect the safety of the persons concerned and their triggering circumstances will be reported as soon as possible to the concerned regulatory authorities and the ECs, if applicable.

Periodic safety reporting to regulatory authorities and the IECs will follow pertinent national legislation.

#### Follow Up:

All SAEs judged to be related to the investigational medicinal product must be followed by the investigator until their conclusion or until the investigator determines that the patient's condition is stable. All other ADRs must be followed by the investigator until the conditions mentioned above are met or until Day 196±5 or 28±5 Days after End of Treatment Visit, whichever comes first, and until all ADR-related queries for the subject have been resolved. The investigator will take all appropriate and necessary therapeutic measures required for resolution of the ADRs, if applicable. All efforts to collect follow-up information must be documented in the source data.

## 5.6.2 Database Management and Quality Control

The study will be monitored by the Clinical Monitor, and/or representatives of CLINUVEL, or its delegated representative, as frequently as is necessary to determine that data recording and protocol adherence are satisfactory.

The detailed procedures for data entry, data coding, cleaning and electronic data transfer will be provided in a Data Management Plan.

#### 5.7 Statistical Methods and Determination of Sample Size

#### 5.7.1 Statistical and Analytical Plans

A formal statistical analysis plan will be prepared prior to completion of the study and before data analysis is undertaken.

## 5.7.2 Efficacy Assessment

#### 5.7.2.1 Specification of Efficacy Endpoints

Efficacy of the treatment will be assessed by:

- CGIC
- IGA of disease severity using an 11-point VAS (VAS IGA);
- Static IGA of disease severity on a 5-point scale (5-point IGA);
- Patient's Global Assessment of disease severity evaluating skin fragility using a VAS;
- PGIC

•	Number of new skin lesions			
	as counted by the Investigator			
•	Quality of Life,			

Patient records
 of outdoors light exposure and trauma.

All the applied instruments will be analysed using appropriate methods to evaluate their suitability to assess changes in skin disease severity,

The PRO instruments will be assessed based on the judgement of the patients on their suitability to document their skin disease. The methodology for analysis of the applied instruments, as well as for assessment of the PRO instruments, will be described in a separate document.

## 5.7.3 Safety Assessment

## 5.7.3.1 Specification of Safety Endpoint

The safety endpoint will be the incidence of TEAEs occurring during the study period, including clinically significant changes in laboratory parameters, which will be listed by intensity, seriousness, outcome, and relationship to study drug.

## 5.7.4 Sample Size

A total of six (6) patients are planned to be enrolled in this study,

The data collected from these six patients will inform whether further trials will be needed.

#### 5.7.5 Analysis Plan

#### 5.7.5.1 Safety Population

The safety population will include all subjects who participate in the study and receive at least one study treatment. Participants screened but not enrolled will be shown in separate listings.

## 5.7.5.2 Intention To Treat (ITT) Population

The ITT population will include all treated participants, who provide at least one post dose efficacy assessment. This will be the main population for all efficacy analyses.

5.7.5.4 Per Protocol Analysis (PPA) Population  5.7.5.5 Demographic and Initial Characteristics  Demographic and baseline characteristics will be summarised using descriptive statistics.  5.7.5.6 Efficacy  Primary and secondary efficacy endpoints are described under section 5.5.3.1 Efficacy variathe Study Protocol.	
5.7.5.4 Per Protocol Analysis (PPA) Population  5.7.5.5 Demographic and Initial Characteristics  Demographic and baseline characteristics will be summarised using descriptive statistics.  5.7.5.6 Efficacy  Primary and secondary efficacy endpoints are described under section 5.5.3.1 Efficacy var	
5.7.5.4	Per Protocol Analysis (PPA) Population
5.7.5.5	Demographic and Initial Characteristics
Demographic and	baseline characteristics will be summarised using descriptive statistics.
5.7.5.6	Efficacy
5.7.5.4 Per Protocol Analysis (PPA) Population  5.7.5.5 Demographic and Initial Characteristics  Demographic and baseline characteristics will be summarised using descriptive statistics.  5.7.5.6 Efficacy  Primary and secondary efficacy endpoints are described under section 5.5.3.1 Efficacy variations.	

i

Since this study is in a rare disease, the clinical relevance of changes in the study endpoints has not yet been established, and so a minimal clinically importance change is not defined *apriori*. Further details will be included in the statistical analysis plan.

5.7.5.7 Safety

Descriptive methods will be used to summarise the safety data. These will be based upon the safety population.

#### 5.7.5.8 Adverse Events

All AEs, including non-TEAEs, will be listed. A TEAE is defined as:

- An event that was not present prior to or on the day of the first study medication administration but was present after study medication was administered.
- An event that was present prior to first administration of study medication and continued to occur after the administration of the first dose at an increased level of severity.
- An event that was present prior to administration of study medication and was documented as completely resolved and re-emerged after the administration of the first dose.

The MedDRA dictionary (Version 23.0) will be used to map verbatim AE terms to preferred terms and body systems. The number of participants with TEAEs will be summarised by preferred term and body system. TEAEs will be further summarised by intensity, seriousness and relationship to study medication. The number of participants who terminate treatment early due to AEs related to study medication will be tabulated. Summaries of the incidence of toxicities will be prepared, as appropriate.

SAEs and SUSARs will be listed individually. Any SAE that occurs after the first dose of the study medication, will be documented in the study report.

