#### 5.3.6 Compliance

Data related to the administration of the study drug will be recorded on the CRF.

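### As worded, the TEAE definition excludes new adverse events that start after dosing on the first dosing day, so the TEAE incidence endpoint omits them

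*Combined protocol and SAP*

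**What the plan says.** Section 5.7.5.8 gives three alternative routes by which an adverse event becomes treatment-emergent:

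1. New events: "An event that was not present prior to or on the day of the first study medication administration but was present after" (that is, after dosing).
2. Worsening events: present before the first administration, and "continued to occur after the administration of the first dose at an increased level of severity".
3. Re-emerging events: "An event that was present prior to administration of study medication and was documented as completely resolved and re-emerged after" the first dose.

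The definition decides what is counted. Section 5.7.3.1 states: "The safety endpoint will be the incidence of TEAEs occurring during the study period". Section 5.7.5.8 adds: "The number of participants with TEAEs will be summarised by preferred term and body system", with further summaries of TEAEs by intensity, seriousness and relationship. The same section also provides that "All AEs, including non-TEAEs, will be listed".

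On timing data, section 5.5.3.2.6 has the investigator "assess the AE(s) in the patient's medical notes and provide the date and time of onset", and section 5.3.6 says: "Data related to the administration of the study drug will be recorded on the CRF". Section 5.7.1 promises a formal SAP before analysis. No other definition of a TEAE is visible in the text supplied.

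**The concern.** The first criterion draws its line at the calendar day of first dosing, not at the dose. It therefore removes the hours straight after the first exposure, when any immediate reaction to the administration would appear. The other two criteria and the sentence on serious adverse events all refer to the first dose, so the first criterion is the odd one out.

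The result is inconsistent. An event already present before dosing that gets worse afterwards on the same day counts as treatment-emergent. An event that is entirely new after dosing on that day does not, and it stays excluded if it persists or worsens later, because the worsening criterion needs presence before the dose.

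Safety and tolerability is a secondary objective (section 4.2), and TEAE incidence is its endpoint. A drug-related event on the first day would be absent from the tables by preferred term, body system, intensity, seriousness and relationship.

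**Working it through.** **Inputs.** The three criteria in section 5.7.5.8, the endpoint in section 5.7.3.1, and six planned patients (section 5.7.4). The plan gives no figure to reproduce on this point.

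**Step 1: test cases against the criteria.**

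| Event | Criterion 1 (new) | Criterion 2 (worsening) | Criterion 3 (re-emerging) | TEAE? |
|---|---|---|---|---|
| New, starts after dosing on the first dosing day, occurs once | Fails: present on that day | Fails: not present before the first dose | Fails: no earlier presence, resolution and return | No |
| The same event, starting the next day | Met | – | – | Yes |
| Starts before dosing on the first dosing day, worsens after | Fails | Met | – | Yes |
| Starts before dosing on that day, resolves, returns after | Fails | – | Met | Yes |

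Two details of wording do not change the first row.

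- Criterion 1 ends by requiring presence after administration. That is a second condition joined to the first, so it does not cancel the exclusion of the whole dosing day.
- Criterion 3 does not say *first* where it refers to presence before administration. Read broadly, it might admit a first-day reaction that resolves and comes back after a later dose. It cannot admit one that occurs once.

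**Step 2: effect on the overall count.** Assume that all six planned patients are treated. A patient whose only event is of this kind drops out of the numerator:

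1/6 = 0.167, or 16.7 percentage points per patient.

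The documents give no frequency for such events, so the number of patients affected could be anything from 0/6 to 6/6.

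**Step 3: effect on one row of the preferred-term table.** A patient with another TEAE stays in the overall count. That patient is still lost from the row for the affected term, unless the same term occurs again as a new event on a later day. For one affected patient, with exact (Clopper-Pearson) 95% intervals:

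- Counted: 1/6 = 16.7% (0.4% to 64.1%).
- Not counted: 0/6 = 0% (0% to 45.9%), where the upper limit is 1 − 0.025^(1/6) = 0.459.

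The row goes from one patient to none, so the term disappears from the table.

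**Step 4: what is not affected.** The listing of all adverse events, the individual listing of SAEs and SUSARs, the reporting of any SAE after the first dose, and the tabulation of early terminations due to related events are not limited to TEAEs. The toxicity summaries are not restricted to TEAEs either.

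**The case against.** The strongest reply is that the intent can be read from the section. The first criterion closes on presence after administration, and the other two divide events before and after dosing. The reference to the dosing day may have been meant only for events that began earlier that day, and a sensible analyst may apply it that way. The SAP is still to be written and could settle the point. The study is open-label and single-arm, safety is summarised descriptively, and no visible test or threshold depends on the TEAE count. With six patients, a reader can go through the full listing. The 16.7 points are what any one patient in six is worth and say nothing about whether the case will arise. The two intervals overlap heavily, and the visible text plans none for TEAEs.

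Much of this stands as a limit on importance. The events are not lost from all reporting, their frequency is unknown, and the intervals only show what happens to one row. None of it removes the defect. A listing does not correct a named endpoint. Likely intent does not bind a programmer who applies a date rule as written, and without a correction the classification could be settled after the data have been seen. An SAP that copies the wording repeats the error, and one that departs from it conflicts with the protocol.

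**Conclusion.** The concern holds. Under the protocol's wording, a single new adverse event that starts after dosing on the first dosing day is not a TEAE and is left out of the safety endpoint and its summaries. The bias is downward only and limited to that day. Each patient with no other TEAE lowers overall incidence by 16.7 points, assuming six treated patients; how many would be affected cannot be estimated from the documents.

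The conclusion concerns the protocol text, since no separate SAP is visible. It should be fixed: this is a stated rule that gives a wrong count, in the definition on which the safety endpoint rests, and the correction is close to free.

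**What to change.** - Reword the first criterion along these lines: *an event that was absent before the first administration of study medication and started at or after the date and time of that administration*. The other two criteria can stay as they are.
- Make sure the CRF captures the time of the first administration and the time of onset of each adverse event.
- State that a first-dosing-day event counts as treatment-emergent when the order of onset and dosing cannot be established. This is a convention, chosen so that any error is towards over-counting.
- Use identical wording in the SAP.

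**Cost.** One sentence in each document, plus the short rule for unknown order. Onset date and time already go in the medical notes, and administration data already go on the CRF. The visible text does not say that either time is a CRF field, so up to two fields may have to be added. Reported TEAE incidence may be slightly higher. Dosing and patient management do not change.
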